11.2 Sample Size Calculation

For the pilot study, we have powered our study to address hypothesis 4 above. Our power calculation is as follows: With a total of 60 participants, 20 patients in each cohort, the study will have the statistical power to detect clinically meaningful differences in both engagement in care (appointment adherence) and undetectable viral load at 6 months. Depending on appointment adherence and undetectable viral load in the standard of care control group, we will be able to detect a minimum 40% difference, assuming 80% power and type 1 error probability (alpha) = 0.05. Estimates from our study sites suggest that undetectable viral load can be as low as 50% at any given time in our high-risk population. If we observe this level in the standard of care control group at 6 months, we will be able to observe a difference of 40% (or 90% vs. 50%) between the Cohort 1 CAB-RPV LA in the CBOc arm vs. the Cohort 2 CAB-RPV LA in the clinic arm and Cohort 1 CAB-RPV LA in the CBO arm vs. Cohort 3 no CAB-RPV LA arm participants, respectively. Because our intention to treat (ITT) analytic approach may mean an even lower proportion in controls (because missing data will be considered detectable), we believe our sample size is sufficient to yield rigorous clinical outcomes.

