5.0 Study Subject Selection

5.1 Subject Inclusion Criteria

Cohort 1: Age \geq 18 years, English or Spanish speaking, HIV-positive, labs indicate that they are a candidate for the medication and virally suppressed, meaning that their HIV-1 ribonucleic acid is less than 50 copies per mL. Individuals enrolled in Cohort 1 must be willing to complete the locator form (Appendix G) in order to receive appointment reminders prior to their monthly/bi-monthly injection and ongoing follow-up by outreach and study staff to maximize potential for adherence.

Cohort 2: Currently enrolled in care at CID and receiving CAB-RPV LA injection, age \geq 18 years, English or Spanish speaking. Individuals enrolled must be willing to complete the locator form in order to receive appointment reminders prior to follow-up data collection.

Cohort 3: Enrolled in care at CID but not receiving CAB-RPV LA, age \geq 18 years, matched to participants demographically and in terms of other characteristics in Cohort 1 at a 1:1 ratio. Individuals in Cohort 3 will be receiving the Standard Care for HIV treatment in CID. Standard of care for this group includes access to regular appointments with their HIV provider, oral ART, case management services, etc. Individuals enrolled must be willing to complete the locator form in order to receive appointment reminders prior to follow-up data collection.

Our goal for all three cohorts is to enroll a percentage of women that is equivalent to the number of female patients served by the sites, approximately 20-30% female. Similarly, we will ensure that our sample includes individuals of color proportional to their representation within the setting across all three cohorts.

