7.2 Cohorts 2 & 3 Recruitment, Screening & Enrollment

Cohort 2 Recruitment and Enrollment: Participants for Cohort 2 will be individuals who are receiving HIV in care at BMC's Center for Infectious Diseases (CID) and are receiving CAB-RPV LA. CID pharmacists and providers will approach all individuals who are actively receiving CAB-RPV LA and assess whether they are interested in participating and ask them to complete the Screening Consent (Appendix C). If individuals are interested in participation, they will be given a warm handoff to study staff. Study staff will meet with patients at CID to complete the enrollment consent form (Appendix D). Participants will also be asked to complete the participant questionnaire at the baseline, midpoint (2-4 months post baseline) and endpoint (at least 6 months post baseline). They will also be asked to complete the Locator Form (Appendix F). Participants will enter the cohort and contribute data to the study from their first CAB-RPV LA injection and be followed in the EHR for a period at least 6 months to determine engagement in care and adherence. Data on clinical endpoints (appointment adherence, viral load, CD4, drug use etc.) will be collected from the EHR.

Cohort 3 Recruitment and Enrollment: EHR data will be used to match patients for Cohort 3 1:1 to patients in Cohort 1 based on the following variables: history of drug use, housing status, sex. Patients in cohort 3 will be a prospective cohort of patients who are HIV positive and not receiving CAB-RPV LA. The Clinical Data Warehouse will match 10 participants to every 1 enrolled in Cohort 1 based on the variables above. CID staff will approach potential participants to assess interest in participation. If individuals are interested in participating, they will be given a warm handoff to the project manager to complete the Enrollment Consent form (Appendix D). They will also be asked to complete the Locator Form (Appendix G). The remainder of their study activity will mirror that of Cohort 2.

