7.3 Data Collection

Objective 2 will include two forms of data collection: 1) participant questionnaires at enrollment (baseline), midpoint (2-4 months), and endpoint (at least 6 months post enrollment) follow-up; 2) clinical and appointment data from the EHR. The baseline questionnaire will be administered to all participants at the time of consenting to participate in the study in order to collect basic sociodemographic characteristics, such as gender identity, education, marital status, income, residence, and other characteristics shown to influence ART outcomes (Mills et al., 2006). The questionnaire will also collect data on potential predictors of intervention success, including unmet needs, satisfaction with care and stigma. (Appendix F). At the midpoint (2-4 months post enrollment) and endpoint (at least 6 months post enrollment), the data will be collected again, using the same data collection instrument. The midpoint data collection and endpoint data collection target dates will be determined by study staff and participants at the first enrollment appointment. For Cohort 1 and Cohort 2 participants, these dates will coincide with their scheduled injections if possible, for convenience.

One week before each target data collection date, study staff will contact the participant using the preferred communication method they specified on their Locator Form at enrollment. Once a data collection date has been determined, study staff will contact participant through their preferred means of communication one day prior to appointment for a reminder.

At the time of data collection, the participant and study staff will meet at determined study location (either Project Trust or CID). Study staff will bring the Participant Folder, Log Book and a ClinCard. The participant will complete the participant survey. If the participant is in Cohort 1 or 2 and is scheduled to receive their

Protocol Title: **CAB-RPV LA Implementation Strategies for High-Risk Populations**

injection at this appointment, the survey can be completed during the 15-minute observation period after the injection.

The clinical and appointment data to be collected from the EHR on all study participants will include clinical endpoints (appointment adherence, viral load, CD4, etc.). Data on clinical endpoints will be collected from their EHR at enrollment at each data collection period using the Chart Review Tool (Appendix E).

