7.11 Clinical Management of Participants

Many patients will already be Boston Medical Center patients, and will continue to see their usual Infectious Disease provider during the entirety of the study. Clinical decisions

Protocol Title: **CAB-RPV LA Implementation Strategies for High-Risk Populations**

around patients and the clinical management of missed doses, serious adverse events and adverse events will be managed by the Infectious Disease clinical providers who are on the study staff. Participants who are new to Boston Medical Center will have a new patient MRN assigned to them, and will be assigned to the clinical patient panel of one of the CID providers on the study staff. All clinical decisions about patients will be made by their healthcare providers. Whether to continue or discontinue Cabenuva if a participant becomes pregnant will be decided by the study clinicians in collaboration with the participant's CID provider that will also include a full review of the participant's case and medical record. All participants will continue to be offered all their regular services as before, including care in the CID, relapse prevention and harm reduction services, STI education and counseling, and all other needed services. Study staff will monitor for depression using the same procedures as CID.

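### H3 does not say which appointments count towards appointment adherence, so reminded injection visits in Cohort 1 could be set against routine visits in Cohort 3, and adjustment for prior attendance is optional.

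*Combined protocol and SAP*

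**What the plan says.** Section 11.1 (H3) predicts better engagement in care at 6 months in Cohort 1 than in the matched controls of Cohort 3, and attributes it to the change of service site. The one operational meaning given for engagement is in Section 11.2, which claims power for "clinically meaningful differences in both engagement in care (appointment adherence) and undetectable viral load at 6 months". Section 11.3 models it by logistic regression in events/trials form, so every counted appointment is a trial. Covariates enter on p ≤ 0.2 in bivariate analysis or on clinical significance.

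The cohorts have different visit streams.

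- **Cohort 1.** Participants complete a locator form so as to receive "appointment reminders prior to their monthly/bi-monthly injection and ongoing follow-up by outreach and study staff" (Section 5.1). Section 7.1 sets contacts one week and one day before each injection. Section 7.7 adds staged outreach after a missed one, including street outreach. Existing patients of the medical center also "will continue to see their usual Infectious Disease provider during the entirety of the study" (Section 7.11).
- **Cohort 3.** Section 5.1 gives this cohort regular appointments with an HIV provider. The only study reminders described for it are for data collection.
- **Surveys.** These carry a payment card for all cohorts. "For Cohort 1 and Cohort 2 participants, these dates will coincide with their scheduled injections if possible" (Section 7.3), so some Cohort 1 injection visits are also paid survey visits.

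On baseline, Section 7.3 lists appointment adherence among the clinical endpoints and states: "Data on clinical endpoints will be collected from their EHR at enrollment at each data collection period". No look-back period is given. Section 7.2 matches Cohort 3 to Cohort 1 "based on the following variables: history of drug use, housing status, sex".

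**The concern.** With an events/trials outcome, the choice of appointments determines the result. If injection visits count, most of Cohort 1's trials could be visits that Cohort 3 cannot have, backed by reminders and outreach. A positive H3 could then restate injection receipt, which H2 already measures, while being read as better engagement in HIV care generally. Leaving the set of visits open also allows it to be settled after the data are seen.

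Baseline is a second route to the same difficulty. Cohort 1 is recruited at a drop-in center, a substance use urgent care clinic and a community program (Section 7.1). Cohort 3 is drawn from people already in care at the HIV clinic (Section 5.1). Prior attendance may well differ between them, in a direction the documents do not reveal. Nothing in the matching or the model ensures that it is taken into account.

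**Working it through.** **1. The plan's own figure.** Section 11.2 gives "With a total of 60 participants, 20 patients in each cohort", "assuming 80% power and type 1 error probability (alpha) = 0.05", and 90% vs 50%. Taking a two-sided test with pooled variance (sidedness is not stated):

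n = [1.96·√(2·0.7·0.3) + 0.842·√(0.5·0.5 + 0.9·0.1)]² / 0.4² = (1.270 + 0.491)² / 0.16 ≈ 19.4, so 20 per cohort. Power at 20 is 81.3%.

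The figure reproduces, but for one yes/no result per person. The rates are those for undetectable viral load. No rate is given for appointment adherence, and the calculation is not for a visit-level outcome.

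**2. Injection visits in Cohort 1**, counted from the regimen table in Section 7.0:

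| Path | Months with an injection | By month 6 | By month 7 |
|---|---|---|---|
| No lead-in, monthly | 1 to 7 | 6 | 7 |
| No lead-in, bi-monthly | 1, 2, 4, 6 | 4 | 4 |
| Lead-in, monthly | 2 to 7 | 5 | 6 |
| Lead-in, bi-monthly | 2, 3, 5, 7 | 3 | 4 |

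**3. Effect of counting them.** Let m routine visits be kept at rate p in both cohorts, and k injection visits be kept at rate q in Cohort 1 only. With routine care unchanged:

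gap = (m·p + k·q)/(m + k) − p

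The documents give no attendance rates and no routine visit count. Assume m = 2 and p = 60%.

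| q | k = 4 | k = 6 |
|---|---|---|
| 90% | (1.2 + 3.6)/6 = 80.0%, gap +20.0 | (1.2 + 5.4)/8 = 82.5%, gap +22.5 |
| 80% | (1.2 + 3.2)/6 = 73.3%, gap +13.3 | (1.2 + 4.8)/8 = 75.0%, gap +15.0 |
| 60% | gap 0 | gap 0 |
| 50% | (1.2 + 2.0)/6 = 53.3%, gap −6.7 | (1.2 + 3.0)/8 = 52.5%, gap −7.5 |

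At the ends of the schedule range, k = 3 gives +12 to +18 points and k = 7 gives +15.6 to +23.3 points for q of 80% to 90%.

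The gap depends on p. With p = 70% and q = 80% it is about +6 to +7.5 points (k = 3 to 6). With p = 50% and q = 80% it is +18 to +22.5 points.

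**4. Would such a gap be declared significant?** A visit-level events/trials Wald test was simulated with 20 per cohort, m = 2 and p = 50%. The ranges span within-patient correlation of 0 and 0.2.

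| q | k = 4 | k = 6 |
|---|---|---|
| 80% | 61-63% | 74-77% |
| 50% (no gap) | 6-9% | 5-10% |

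**5. The p ≤ 0.2 screen for prior attendance.** Treat prior engagement as yes/no and assume true rates of 50% vs 65%, with 20 per cohort and a Pearson test. Summing the binomial probabilities of all outcomes with p ≤ 0.2 gives 39.5%. The difference would go unflagged about 60% of the time. At 50% vs 70% it is flagged 53% of the time.

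**The case against.** A reader might infer that H3 does mix the two visit types and that a false gap would follow. The documents do not support that.

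- **The definition is missing, not wrong.** Section 10.1 says that injections received are recorded in the EHR. Adherence also needs scheduled and missed visits, and next injection dates and missed-dose contacts go into the study log book (Sections 7.1, 7.6 and 7.7). The chart review tool (Appendix E) is not in the text available here. Clinical question B2 in Section 1.2 names engagement in services and receipt of injection visits side by side, which can be read either way.
- **The direction is not fixed.** The gap is positive only if injection visits are counted and kept more often than routine ones. Reminders and outreach make that plausible but do not establish it.
- **A baseline value is collected.** It would be wrong to say that none is required, because Section 7.3 provides for it at enrollment. The clinical-significance route in Section 11.3 also allows it into the model. What is missing is a look-back window and a commitment to use it.
- **Attending for injections is arguably engagement.** The study tests bringing treatment to the patient, with reminders and outreach as part of the means. Scoring H3 on provider visits alone could discard what the strategy is meant to achieve.
- **The screening figure is illustrative.** Attendance analysed as a proportion would go through a t-test or Wilcoxon test, with different sensitivity.

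All of these stand. They limit the point to an undefined outcome and an optional adjustment, and they argue for reporting both versions of H3 rather than replacing one with the other. They do not supply the missing definition.

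**Conclusion.** The point holds as a gap in definition and adjustment. Sections 11.1 to 11.3 do not say which appointments or what window make up appointment adherence, and only Cohort 1 has a reminded injection stream. Under the assumed inputs (2 routine visits kept at 60%, 4 to 6 injection visits kept at 80-90%), counting injections could produce a gap of 13 to 22.5 points with routine care unchanged. Equal attendance gives zero and poorer injection attendance gives a negative gap. It cannot be said from the documents that this bias is present.

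The baseline part does not depend on how visits are counted. Recruitment settings differ, prior attendance is not matched on, and at 20 per cohort a p-value screen is a weak way to find an imbalance.

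The change should be made, but it does not threaten the main aim: Section 11.2 powers the pilot on H4. H3 is still a named hypothesis, and as written a positive result could not be interpreted.

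**What to change.** 1. In Section 11.3, make pre-enrollment appointment adherence, over one stated look-back window, a mandatory covariate in the H3 model rather than leaving it to the p ≤ 0.2 screen. For newcomers to the medical center, use the care history obtained under the release of information in Section 7.1.
2. In Sections 11.1 and 11.3, define the counted appointments and the counting window identically for Cohorts 1 and 3.
3. Report H3 twice: on visit types that both cohorts have, and on all visits including injections. Interpret a gap seen only in the second as injection attendance, not as improved routine engagement.

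**Cost.** This needs analysis plan wording and a visit-type filter in the EHR extract, with no new participants or visits. The common-visit analysis is less precise. With 2 routine visits each there are 40 visits per cohort, and at 60% kept the 95% half-width is 1.96·√(0.24/40 + 0.24/40) ≈ 21 points. Adding 6 injection visits gives Cohort 1 160 visits, and at the same rate the half-width is 1.96·√(0.24/160 + 0.24/40) ≈ 17 points. Both ignore within-patient correlation.

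Two practical limits remain. Prior history may be incomplete for newcomers. Injection and provider visits may also overlap in the EHR coding, because injections are given by the medical center's own clinicians (Section 6.0) and newcomers join the panel of a clinic provider on the study staff (Section 7.11). A rule for coding such visits should be written before data extraction.

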11.0 Statistical Plan

11.1 Study Hypotheses

Objective 2 has the following hypotheses:

- **H1:** Changing the service site will result in $\geq 80\%$ of participants in the community-based intervention arm beginning injections
- **H2:** Of participants in the community-based intervention arm who begin injections, 80% will complete 6 injections
- **H3:** Changing the service site will result in improved engagement in care for participants in the community-based intervention arm compared to matched controls (Cohort 3) at 6 months for intervention patients compared to control group patients
- **H4:** Changing the service site will result in superior HIV viral suppression at 6 months compared to for participants in the community-based intervention arm compared to matched controls (Cohort 3)
- **H5:** Participants in the community-based intervention arm will be equally satisfied with their care compared to patients who receive care in clinic settings (Cohort 2).

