11.3 Statistical Methods

We will first conduct exploratory analyses to assess the completeness and distributional properties of all variables, including an exploration of location (e.g., means for continuous variables and frequencies and percentages for categorical variables), spread (e.g., ranges, standard deviations), and shape (e.g., normal, skew). Missing baseline sociodemographic data will be imputed using single or multiple imputation technique if the proportion missing is $<10\%$ or $\geq 10\%$, respectively. After enrollment, we will compare dropout rates and characteristics of subjects who drop out or are lost to follow-up to assess potential for bias. In cases of missing viral load data, we will treat the result as detectable, in accordance with our primary ITT analytic approach, similar to other studies. Our primary analyses will be by ITT, but we will also conduct per protocol analyses via logistic regression models to estimate treatment effects.

Sociodemographic, behavioral, and clinical attributes at baseline will be compared between Cohort 1 and Cohort 2 and Cohort 1 and Cohort 3 using Chi Square and Fisher Exact test for categorical variables and T-test and Wilcoxon and Kruskal-

Protocol Title: **CAB-RPV LA Implementation Strategies for High-Risk Populations**

Wallis tests for continuous variables. Differences in engagement in care will be examined in two separate models to compare Cohort 1 vs Cohort 2 and Cohort 1 vs. Cohort 3. We will construct a multivariable logistic regression model with a logit link and the events/trials syntax to model the outcome. The inclusion of key baseline variables for adjustment will be based on a p value of ≤ 0.2 in the bivariate analysis or clinical significance. The following regression equation will be used:

$$\text{Engagement in care} = \alpha + \beta_1 * \text{ixgroup}_1 + \beta_2 * \text{factor}_1 + \dots + \beta_n * \text{factor}_n + \varepsilon,$$

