where ixgroup_1 is a dummy variable for cohort assignment, α is the intercept, $\beta_1, \beta_2, \dots, \beta_n$ is a vector of possible coefficients, and ε is an error term. Similarly to examine adherence we will use a multivariable logistic regression with a dichotomous outcome for undetectable viral load status at 6 months. Potential confounders will be examined using methods described above and entered into the final model based on a p value of ≤ 0.2 or clinical significance. We will conduct stratified analyses based on gender and other risk attributes (e.g. homelessness, substance use, etc.), though this will be exploratory, given the cohort study's pilot nature and our sample size.

12. Budget Justification

Our total enrollment into Objective 2 remains 60 participants. Therefore, the resources necessary to accomplish the scope remain unchanged, and we are not requesting a budget increase.

13. Ethics/Protection of Human Subjects

This study will be conducted according to applicable US federal regulations and institutional policies (which are based in federal regulations, guidance, and ICH Good Clinical Practice guidelines). This protocol and any amendments will be submitted to the Boston Medical Center/Boston University Medical Campus IRB, for formal approval of the study conduct. The decision of the IRB concerning the conduct of the study will be made in writing to the investigator.

All subjects for this study will be provided a consent form describing this study and providing sufficient information for subjects to make an informed decision about their participation in this study. The consent form will be submitted with the protocol for review and approval by the IRB. The consent of a subject, using the IRB-approved consent form, must be obtained before that subject is submitted to any study procedure. Consent will be documented as required by the IRB.

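### The 80% power for H4 assumes complete viral-load data, yet missing-equals-detectable is cited as support although it lowers every cohort; Cohort 2 is also given the standard-of-care 50%

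*Combined protocol and SAP*

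**What the plan says.** H4 in section 11.1 is a superiority hypothesis: "Changing the service site will result in superior HIV viral suppression at 6 months", for the community arm against the matched controls in Cohort 3. Section 11.2 names H4 as the hypothesis the study is powered for. With 20 participants per cohort, it says "we will be able to detect a minimum 40% difference, assuming 80% power and type 1 error probability (alpha) = 0.05".

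The control rate of 50% is a site estimate for the high-risk population. It is introduced with the condition "If we observe this level in the standard of care control group at 6 months". The resulting 90% versus 50% contrast is then claimed for two comparisons: Cohort 1 versus Cohort 3, and also "between the Cohort 1 CAB-RPV LA in the CBOc arm vs. the Cohort 2 CAB-RPV LA in the clinic arm".

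Section 11.2 closes by saying that the ITT approach "may mean an even lower proportion in controls (because missing data will be considered detectable), we believe our sample size is sufficient".

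Section 11.3 states the missing-data rule without limiting it to any cohort: "In cases of missing viral load data, we will treat the result as detectable, in accordance with our primary ITT analytic approach". For the outcome model, "we will use a multivariable logistic regression with a dichotomous outcome for undetectable viral load status at 6 months".

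**The concern.** The closing argument of section 11.2 uses only the favourable half of the missing-data rule. Counting a missing result as detectable lowers the observed proportion in whichever cohort the result is missing from, and section 11.3 applies the rule to all of them. A reader of 11.2 would conclude that missing data make the design safer. If the two cohorts miss results at similar rates, the opposite is true.

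If Cohort 3 misses more, the rule can hold power up, but it can also create an apparent suppression benefit where none exists. The documents give a reason to expect imbalance. The 6-month result comes from the EHR (sections 6.0 and 7.3). Cohort 1 receives staged outreach after a missed injection (section 7.7). Cohort 3 receives no intervention beyond data collection (section 6.0), although it does get reminders before data collection (sections 5.1 and 7.3).

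Separately, the 50% is a standard-of-care rate, and section 11.2 transfers it to a cohort that is on CAB-RPV LA.

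**Working it through.** **Inputs.** From section 11.2: n = 20 per cohort, rates 0.90 and 0.50, alpha 0.05, power 80%. From section 11.3: missing = detectable. The documents give no missingness rate, no sidedness and no test for the power calculation. I take two-sided 0.05 and unadjusted tests, and every missing rate below is an assumption. With a share m missing, a true rate p is observed as p(1 − m), and the denominator stays at 20.

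**Step 1: the plan's own figure.** With pooled mean 0.70:

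- n = (1.96·√(2·0.7·0.3) + 0.842·√(0.09 + 0.25))² / 0.4² = (1.270 + 0.491)² / 0.16 = 19.4, so 20 per cohort.
- Power at n = 20: Φ[(0.4 − 1.96·√0.021) / √0.017] = Φ(0.89) = 81%.

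Exact enumeration of all 21 × 21 outcomes gives 84% for the uncorrected chi-square test. The stated figure therefore reproduces for complete data.

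**Step 2: equal missingness in Cohorts 1 and 3.** The gap becomes 0.9(1 − m) − 0.5(1 − m) = 0.4(1 − m).

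| Missing in both (assumed) | Observed rates | Normal approx. | Chi-square | Fisher | Logistic Wald* | n per cohort for 80% (normal approx.) |
|---|---|---|---|---|---|---|
| 0% | 90.0 vs 50.0 | 81% | 84% | 74% | 69% | 20 |
| 5% | 85.5 vs 47.5 | 74% | 76% | 65% | 68% | 24 |
| 10% | 81.0 vs 45.0 | 67% | 68% | 56% | 63% | 28 |
| 20% | 72.0 vs 40.0 | 53% | 52% | 40% | 50% | 37 |

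*Tables with 0 or 20 successes in a cohort are counted as non-significant. See the objection below.

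By normal approximation, power drops below 80% at about 1% missing, so there is essentially no slack.

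**Step 3: unequal missingness.** Let m1 and m3 be the missing shares in Cohorts 1 and 3. The gap stays at 40 points when 0.9(1 − m1) − 0.5(1 − m3) = 0.4, that is, when m3 = 1.8·m1. Chi-square power of 80% needs m3 of about 9%, 22% or 44% when m1 is 5%, 10% or 20%. Examples, m1 vs m3:

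- 5% vs 20%: 88%
- 10% vs 25%: 82%
- 10% vs 20%: 78%

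**Step 4: what unequal missingness does when there is no true difference.** If both cohorts have true rate p, the expected spurious gap is p(m3 − m1). At 5% vs 20% missing this is 0.5 × 0.15 = 7.5 points, or 0.9 × 0.15 = 13.5 points. Chi-square false-positive rates:

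| Missing, Cohort 1 vs Cohort 3 (assumed) | True rate 50% in both | True rate 90% in both |
|---|---|---|
| none | 4% | 4% |
| 5% vs 10% | 5% | 7% |
| 5% vs 20% | 7% | 18% |
| 5% vs 30% | 12% | 38% |

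**Step 5: Cohort 1 versus Cohort 2.** The Protocol Summary lists Cohort 2 as virally suppressed at enrollment, and section 5.1 requires that it is already receiving CAB-RPV LA. No 6-month rate for Cohort 2 is given. With Cohort 1 at 90% and Cohort 2 at an assumed 50%, 60%, 70% or 80%, chi-square power is 84%, 62%, 36% or 14%. The documents support none of these Cohort 2 rates.

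**The case against.** The strongest reply is that equal missingness is the less likely case. Cohort 1 has injection reminders and outreach that Cohort 3 lacks, so Cohort 3 may well miss more results, and then power can stay above 80% (81% by chi-square at 5% vs 10%, 88% at 5% vs 20%). That is true. But section 11.2 gives no rates to support it, and power gained this way does not come from better suppression.

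A second reply is that missing-equals-detectable is the declared primary rule and that, in a study of engagement, loss to care is arguably part of the outcome. This is a fair reason to keep the rule as primary. It does not make the rule evidence that the sample size is sufficient for H4, which is worded as viral suppression.

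Third, section 11.3 already plans completeness checks and per-protocol analyses, and says "After enrollment, we will compare dropout rates and characteristics of subjects who drop out or are lost to follow-up to assess potential for bias". These help describe the problem. None is said to treat a missing 6-month viral load differently, and the planned imputation covers baseline sociodemographic data only.

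Two cautions on the numbers stand. The 69% Wald figure depends on how separated tables are counted: at 90%, Cohort 1 reaches 20 of 20 in 0.9²⁰ = 12% of samples. A logistic likelihood-ratio test gives 84%, and a Wald test with 0.5 added to each cell gives about 77%. Also, the 18% and 38% false-positive rates need 90% true suppression in Cohort 3, well above the plan's own 50%; at 50% the corresponding figures are 7% and 12%.

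Finally, the study is a pilot, the sentence is hedged, and the Cohort 2 claim does not affect H4. These points limit the severity, but section 11.2 still makes a specific power claim that does not match the planned analysis.

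**Conclusion.** The concern holds. There is no error in the calculation itself: 20 per cohort gives 81% to 84% power for 90% versus 50% when every viral load is available, by the normal approximation or chi-square. The error lies in offering missing-equals-detectable as support while applying it in thought to controls alone. At assumed equal missingness of 5% to 20%, chi-square power is 76% to 52%. The direction depends on relative missingness, for which the documents give no figures, so the size of any loss is unknown. Where power is kept by higher missingness in Cohort 3, the same mechanism raises the false-positive rate.

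The Cohort 1 versus Cohort 2 power claim has no basis in the documents, and no numbered viral-load hypothesis uses that comparison. This should be fixed, but it does not undermine the choice of primary rule.

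**What to change.** 1. In section 11.2, say that the 80% assumes complete 6-month viral-load data. Add a short table of power with the rule applied to both cohorts, over a range of equal and unequal missingness labelled as assumed. Compute it for the test the analysis will use, and name that test.
2. Delete the sentence that uses the ITT rule to support the sample size.
3. Delete the Cohort 1 versus Cohort 2 power claim, or say that this comparison will be reported as an estimate with a 95% confidence interval. Do not insert a Cohort 2 rate without a source.
4. In section 11.3, keep missing-equals-detectable as the primary rule, report the share with a 6-month viral load by cohort, and add a tipping-point or multiple-imputation sensitivity analysis for missing 6-month results.

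The cost is text in two sections and a little extra analysis, with no new participants or visits. The stated power becomes less favourable.
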